5.3 Study procedures

The procedure with patients will go as following:

- An algorithm and the general practitioner both identify eligible patients. This results in two separate, possibly overlapping, lists.
- Lists of patients are screened for inclusion criteria.
- GP checks the list of patients, meeting inclusion criteria, for exclusion criteria. Patients can be grouped in one of three categories: (1) eligible per GP-list and per algorithm, (2) eligible per GP list and (3) eligible per algorithm.
- Internal order of these lists are randomised. First, patients who appear on the list of both GP and algorithm are approached for study participation. Then, recruitment alternates between the GP-list and the algorithm list to acquire a 50/50 divide.
- GP practice approached patient and ask permission/ consent for sharing the contact information with the researchers so they give them written and oral information about the study
- Study information is sent per mail.
- Phone call from researcher to answer questions and acquire informed consent.
- Start control period.
- Baseline questionnaire: The 'cost and care utilization' and EQ-5D-5L questionnaires will be sent out to participants to fill in at home.
- Start of intervention period (including intake and MDO's).
- Questionnaires: Repetition of the 'cost and care utilization' and EQ-5D-5L questionnaires according to schedule as depicted in §3 study design (7 or 8 measurements per patient). Furthermore, four questionnaires (SF-12, UPCC, SE+IN

itemlist, and PAM-13) will be repeated three times (before the start of the intervention, at the end of the intervention and 2 months after the intervention has ended). The remaining two questionnaires (HCCQ and adapted NPS) will be administered once (at the end of the 6 month mark of the intervention).

- All participants are invited to join a focus group 12 months after starting the intervention. Patients will first be informed about the focus group through the patient information form. When a group is near the end of the 12-month intervention period, all patients in this group will be approached by the researchers to confirm participation. The goal of the focus group is to obtain insight about the patients' experience with the new approach. Participation is not obligatory.
- As part of process evaluation all involved professionals (GP, POH-GGZ, social workers or other) will be invited to join a focusgroup on their experience with this proactive, integrated care approach and the audio records of the intake and MDO will be scored on the level of shared decision making by two independent observers.
- Collection of data on: medical and acute care utilization, medical costs. (beginning and end of study).

The following time investment will be asked from each patient:

- 10 minutes: invitation of the patient by the GP practice and sharing of information about the study with the patient. Permission to send information about the study, will be asked.
- 10 minutes: follow-up with patient about participation in the study. If the patient agrees to participate, an informed consent form will be send out.
- 170 minutes for the questionnaires: this consists of 4 timepoints of EQ-5D-5L and Care and work questionnaire (4x10min = 40min), two timepoints of psychological questionnaires(SF-12, PAM-13, SE+IN) with EQ-5D-5L and care and work (2x40min = 80min), once EQ-5D-5L with Care and Work and evaluative questionnaire (modified NPS, HCCQ) (1x 10min = 10 min) and once psychological questionnaires combined with EQ-5D-5L (1x40min = 40min).
- 45 minutes: first consultation based on the Positive Health Methodology.
- 60 minutes (2x30=60min): all patients are invited and stimulated to join the multidisciplinary meetings. Patients will be discussed at least at least 2 times during the 12 month period. Additional ad hoc meeting is possible if necessary.
- 10-30 minutes (minimum of 4 times, thus combined total of 40-120 minutes): for the extra meetings that patients are going to have with their care coordinator, according to their personal care plan.
- 60 minutes: focus group focused on the patients their experience with the intervention. Each focus group will be 60 minutes and each patient will only be invited once. This will be done after they end the intervention.

	First three month period	Total 12 months period	Total in study period
POH-GGZ intake	1x45 min	1x 45 min	1x45 minutes
Multidisciplinary meeting	1x30 min	Minimum 2x 30	Minimum 2x 30 minutes
Care coordinator	Minimum of 3x, more frequent contact is	Minimum of 4x in 12 months, however more	Minimum of 4x in 12 months

	possible. Proactive nature of this contact is highlighted.	frequent contact is expected. Proactive nature of contact is highlighted.	
Questionnaires			170 minutes
Focusgroup			1x60 minutes

During the 22 month study period, the following questionnaires will be sent out per mail, but in case of no response done by interview (see F1):

- EQ-5D-L5 (Versteegh et al., 2016). This will be filled in at a maximum of 8 different timepoints.
- Selected questions from iMCQ, iPCQ and TiC-P. This will also be filled in at a maximum of 7 different timepoints.
- HCCQ and modified NPS (Jochems et al., 2014; Czajkowska et al., 2017; Reichheld, 2003; Krol et al, 2015). This will be filled in at 1 timepoint.

The remaining questionnaires will be filled in during a face to face interview with the researcher or trained intern or research assistant (before the start of the intervention, at the end of the intervention and 2 months after the intervention has ended).

5.4 Withdrawal of individual subjects

Subjects can leave the study at any time for any reason if they wish to do so without any consequences. The investigator can decide to withdraw a subject from the study for urgent medical reasons.

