1. OBJECTIVES

The primary goal of this study is to get insight in the cost-effectiveness after 12 months of working with a proactive, integrated (social) care approach in patients fitting our definition of a hotspotter. A hotspotter is a patient with problems on two out of three health domains (chronic somatic, psychiatric and/or social) and at least 2 acute care activities in the previous 12 months. The medical data from 3 years prior to the start of the study will be used to analyse the costs and utilisation of care. This extended period used for data analysis was deliberately chosen to include a timeframe during and before the SARS-CoV-2 pandemic. Since it is yet unknown how the pandemic and its subsequent measures affected our population and their usage of care.

Hypothesis: We hypothesise that after one year of working with a proactive approach of integrated care to improve the care for patients with problems on two out of three health domains (chronic somatic, psychic and/or social) and at least 2 acute care activities in the previous 12 months will result in reduction in volume and spending of acute care, improvement in experienced health and in patient experience.

Research questions:

Is proactive integrated care cost-effective and result in better patients experience than usual care after 12 months for patients with problems on multiple life domains?

Primary outcomes: Incremental cost-effectiveness from a societal perspective. Information on cost will be based on patient-reported data obtained by questionnaires supplied with data from the GP medical files (*Huisarts informatie system, HIS*) and through CBS microdata. To assess the effectiveness the EQ-5D-5L will be used for determining quality of life.

Secondary outcomes:

Insight into patients experience of care:

Insights into the experiences of care will be gathered during a focus group and information about self-efficacy (PAM-13 and SE+IN itemlist), proactive coping (UPCC), and quality of life (SF-12) will be collected using questionnaires (Hibbard, Mahoney, Stockard, & Tusler, 2005; Bode, & de Ridder, 2008; Turner-Bowker, & Hoque, 2014). A questionnaire on experience of care has been considered, but no validated and appropriate questionnaires for this population are available. Therefore, for insight and rich information on the experienced care the format of a focus group was chosen.

Process evaluation:

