4.2 Inclusion criteria

In order to be eligible to participate in this study, the following criteria must be met by the general practice and participating patients.

GP practice:

- There is a POH-GGZ available in the GP practice.
- Planning of a multidisciplinary meeting (MTM or MDO) is a possibility within the GP practice.
- The GP practice is willing to work and share information with different care professionals in the recurring multidisciplinary meetings, to optimise the results of the intervention.
-

Participants:

- The patients are ≥ 18 yrs
- The patients are registered within one of the participating GP practices.
- Patients with at least two acute care encounters in the past 12 months. Acute care encounter is defined as an encounter with out-of-hours GP service, emergency care, acute mental health care or unplanned hospital admittance.
- Patients have problems registered in the GP Information system on at least two out of three of the following domains: somatic, mental or social. Somatic problems is having at least one ICPC code on the problem list. Mental problems is having at least one ICPC code from the "P"-chapter on either the problem list, as a reason for encounter, and/or having medication prescribed related to mental health problems. Social problems is having at least one ICPC code from the "Z"-chapter or as reason for encounter, and/or having medication prescribed related to social problems.

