5.6 Follow-up of subjects withdrawn from treatment

When a participant chooses to retract from of the study, data collection for that participant will stop. The data collected until the moment of withdrawal will be used when analysing the data, unless the patient specifically requests otherwise.

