5.7 Premature termination of the study

This is not applicable to this study. There are no health risks associated with study.

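### Section 5.4 allows medical withdrawal from the whole study, and the protocol does not separate ending the intervention from ending cost and EQ-5D follow-up

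*Protocol*

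**What the plan says.** Three short sections of the protocol bear on this point.

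- Section 5.4: "The investigator can decide to withdraw a subject from the study for urgent medical reasons". The withdrawal is from the study, not from the intervention. The medical reasons are not defined and the section has no data rule.
- Section 5.6, headed as follow-up of subjects withdrawn from treatment: "When a participant chooses to retract from of the study, data collection for that participant will stop". It continues: "The data collected until the moment of withdrawal will be used when analysing the data, unless the patient specifically requests otherwise".
- Section 5.7, on premature termination: "There are no health risks associated with study".

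The outcome is set in the Objectives chapter: "Primary outcomes: Incremental cost-effectiveness from a societal perspective". The hypothesis there is that the approach "will result in reduction in volume and spending of acute care, improvement in experienced health and in patient experience". Under section 5.1.1, utilisation and cost data come from HIS and CBS records plus patient report, and are collected at t=0 and t=22. EQ-5D-5L is measured by questionnaire at seven or eight timepoints.

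**The concern.** In a trial whose outcome is cost and health, a patient taken out for a serious medical reason is likely to be costlier and in poorer health than average over the following months. If data collection ends at that point, follow-up is lost for reasons related to the outcome. The analysis cannot recover records that were never collected.

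The protocol leaves this open because it treats leaving the intervention and leaving data collection as a single event. Section 5.4.1 lets patients return to usual care, under a withdrawal heading, again without saying whether their data continue. The HIS and CBS records are passive and need nothing from the patient at the time of extraction. The protocol says the study carries no health risk and gives no reason why a medical event should stop that extraction.

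**Working it through.** The protocol gives no number or rate of investigator withdrawals, so there is no figure of its own to reproduce here. The check has three parts.

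**1. The text, case by case**

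| Situation | Intervention contacts | Data before | Data after |
|---|---|---|---|
| Patient chooses to leave the study (5.6) | end | used, unless the patient objects | collection stops |
| Patient returns to usual care (5.4.1) | end | not stated | not stated |
| Investigator withdraws for medical reasons (5.4) | end | not stated | not stated |

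For the third row, the nearest rule is 5.6. Its heading reaches this case and its wording does not. A site or data manager following the text could reasonably stop collection. Because cost data are gathered at t=0 and t=22 (5.1.1), the protocol also does not say whether the t=22 extraction is run for a withdrawn patient, even for the months before withdrawal.

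**2. Where the loss would fall**

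Control periods (section 3, four groups switching every two months from t=2) are 2, 4, 6 and 8 months: mean (2+4+6+8)/4 = 5. Post-switch time is 22 − 5 = 17 months on average, or 17/22 = 77%. If the withdrawal rate per month were the same in both conditions, about three quarters of withdrawals would occur post-switch.

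**3. Illustration of size**

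From section 4.4: mean annual cost 22,494 euro, SD 24,585 euro, target decrease 25%. Assumed: lognormal costs; no true effect; withdrawals from the top-cost decile only and in intervention data only; withdrawal time uniform over the period, so half of each withdrawn patient's cost and time is lost on average; mean cost taken per unit of observed time.

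- Squared coefficient of variation: (24,585/22,494)² = 1.1946. Log-scale variance: ln(2.1946) = 0.786; σ = 0.887.
- Cost share of the top decile: Φ(σ − 1.2816) = Φ(−0.395) = 0.346.
- 20% of that decile withdrawn: cost lost 0.2 × 0.346 × 0.5 = 0.0346; time lost 0.2 × 0.1 × 0.5 = 0.010. Ratio (1 − 0.0346)/(1 − 0.010) = 0.975, a fall of 2.5%.
- 50% withdrawn: cost lost 0.0866; time lost 0.025. Ratio 0.9134/0.975 = 0.937, a fall of 6.3%.

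Against the 25% target these are about one tenth and one quarter. The result depends on the analysis. If missing months were counted as zero cost, the falls would be 3.5% and 8.7%. If each patient's cost rate were annualised with equal weight, and costs ran evenly over time within a patient, there would be no fall. Similar losses in control time would offset the contrast.

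**The case against.** The strongest reply is that the protocol never says data collection stops after a withdrawal by the investigator. Section 5.6 speaks of a participant who chooses to leave, and data up to that moment are kept. Medical withdrawals should also be rare in a study of care coordination and questionnaires. The planned multilevel models can reduce bias where earlier data predict the missing values, and the handling of incomplete follow-up may properly be left to the SAP. The consent pages are not available, so any wording there on continued use of routine records cannot be checked.

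Much of this stands, and it rules out several stronger inferences:

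- A reader might infer that urgent medical reasons are the acute events the trial counts. The protocol makes no such link. Section 4.2 says "Acute care encounter is defined as an encounter with out-of-hours GP service, emergency care, acute mental health care or unplanned hospital admittance", and every patient enters with at least two of these in the past 12 months. Withdrawing patients for them would empty the trial.
- A reader might infer that the costs of the triggering event are discarded. Section 5.6 provides for the use of data up to withdrawal, so at most later costs are at risk, apart from the doubt about the t=22 extraction.
- A reader might infer a bias in favour of the intervention. Intervention contacts could give investigators an extra reason to withdraw a patient, but nothing in the protocol shows a different rate by condition.
- A reader might compute much larger effects by removing the costliest patients altogether: 10% or 18% for the top 2% or 5%, or 5% and 13% if 20% or 50% of the top decile lose all their data. The arithmetic is correct on the lognormal assumption, but complete loss contradicts 5.6.

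What the reply does not remove is the gap itself. Whether records are collected is a protocol matter, and the only rule that comes near this case says to stop.

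**Conclusion.** The point holds as a gap in the protocol. Sections 5.4 and 5.6 together allow cost and EQ-5D follow-up to end after an investigator's medical withdrawal, for reasons related to the outcome, and do not say whether the t=22 extraction still includes the patient. Most of such loss would fall in post-switch time if monthly withdrawal rates are similar in the two conditions.

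Size and direction are unknown. The 2.5% to 6% range is an illustration that rests on the lognormal shape, an assumed 20% to 50% withdrawal within the top-cost decile, loss in intervention data only, and cost per observed time. None of these assumptions comes from the protocol. The documents do not support a claim that the result will be biased towards the hypothesis. This is a worthwhile, inexpensive improvement and not a flaw that undermines the design.

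**What to change.** Leave the clinical decision in 5.4 as it is and define its consequence for data. In 5.4 and 5.6, state that:

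- a medical withdrawal initiated by the investigator ends intervention contacts only;
- HIS/CBS cost and acute-care data continue to t=22, and the final extraction includes these patients;
- EQ-5D-5L continues where the patient is able and willing;
- collection ends early only if the patient withdraws consent;
- the date, the reason and the condition at the time (control or intervention) are recorded.

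The cost is a sentence or two in each section and a few fields on the withdrawal form. The HIS/CBS extraction is already planned. The patient information should be checked to confirm that it covers continued use of routine records. The downside is a few more questionnaire contacts with ill patients, who may decline.

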5.4.1 Specific criteria for withdrawal

The participating patients have the option to revert back to care as usual, at any given time. The reason for withdrawal will be asked, however patients are not obliged to answer if they do not wish to share the reason.

5.5 Replacement of individual subjects after withdrawal

Patients that chose to withdrawal from the study, will not be replaced.

5.6 Follow-up of subjects withdrawn from treatment

When a participant chooses to retract from of the study, data collection for that participant will stop. The data collected until the moment of withdrawal will be used when analysing the data, unless the patient specifically requests otherwise.

5.7 Premature termination of the study

This is not applicable to this study. There are no health risks associated with study.

6. STATISTICAL ANALYSIS

Before analysis, all data will be cleaned improving data quality.

Quantitative data:

We will conduct intention-to-treat and per protocol analysis. We will use multilevel generalized linear models with the patient as the first level to correct for the repeated measures. The GP-practice (or cluster) will be the second level, and the group in which the GP practice is randomized will be the third level. We will adjust for level of integration, neighbourhood, time from start of study (continuous; with an interaction between cluster and time so that each cluster had its own underlying time trend), and total time on the randomised intervention, with time before intervention given as zero (continuous). Based on ICPC-codes used to select eligible patients, we will explore if subgroups can be identified in mainly (chronic) somatic, mainly mental or mainly social problems. Furthermore, analyses/ results will be stratification for sex. The analysis of the implementation will be descriptive.

Cost-effectiveness analysis/budget impact analysis:

The economic evaluation will consist of a trial-based cost-utility analysis (cost per QALY) with a time horizon of one year and a cost-utility analysis with a lifetime horizon (cost per QALY). Both analyses will be performed from a societal perspective. Next to this a Budget Impact Analysis will be performed according to the ISPOR Task Force principles.

Qualitative data:

Qualitative data will be collected through interviews or focus groups with care providers and patients and audiorecording. The interviews and focus groups will be conducted using a topic list based on experience of the pilot (protocol number **NL8223-10216**) and literature, to determine their satisfaction with the new approach.

The collected qualitative data will be analysed using both an inductive and deductive approach. This will be done by first transcribing the data and doing a thematic content analysis. After this, the data will be put into an initial coding book and further analysed until a final coding book is formed. The deductive analysis will be done using the positive health methodology. We will analyze whether positive health topics and techniques are being discussed and applied, as recommended by the methodology.

The audiotapes will be scored by two independent observers using the validated OPTION5 questionnaire.

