3. STUDY DESIGN

We will use a stepped-wedge randomised controlled trial (RCT) design (Hemming, Haines, Chilton, Girling, & Lilford, 2015). This design involves random and sequential crossover of groups from control to intervention until all groups are exposed to the intervention. A stepped wedge cluster RCT is especially useful when the intervention is thought to do more good than harm (i.e., when there is no equipoise). In that situation, it is unethical to withhold or withdraw the intervention from a proportion of the subjects as would occur in a parallel group or classic cluster RCT. Besides, it may be impossible to implement the intervention in half of all clusters simultaneously because of practical, logistical, or financial reasons, which is also the case in the current study with regard to the practical and logistical reasons. Then, the stepwise treatment implementation of the stepped wedge design offers a solution. Since all patients included in this study will be offered the intervention, which may contribute to limiting lost to follow-up

The personalized approach, local collaborations with the social domain and organizational differences between general practices will result in nuanced differences in how our intervention will be applied. Besides, training the Positive Health methodology and the enhanced collaboration between domains most likely effects patients not-offered the intervention as well. Randomisation will therefore be done by cluster.

This study will be performed in 20 general practices. Each practice will form one cluster. We aim to include an average of 10 patients per cluster. A GP or POH-GGZ can only participate in one cluster. The terms GP practice and cluster will be used alternatively and exchangeable from this point on, both referring to the given description.

Each participating patient starts with a control period and will cross-over to the intervention period. The control period varies between 2 to 8 months. All patients from a GP practice cross-over at the same moment. Therefore the GP-practices are randomized into one of four groups.

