All clusters start to collect control data at the same time ($t=0$). The 20 clusters will be divided into four groups evenly and each group will be randomly assigned one of four time points at which they will start to implement the proactive integrated care intervention. The first switch will be after 2 months ($t=2$). Every subsequent 2 months a next group of general practices will switch to the intervention mode until all groups have started the intervention. All groups will continue with the intervention as described in this protocol for a total of 12 months. After the 12 months of intervention, care will be delivered as usual. There is no objection if care providers and patients wish to maintain certain aspects of the intervention. All measurements and timepoints after the switch to the intervention falls under the intervention period. The total duration of this study comprises 22 months. This results in varying control period ranging from 2 to 8 months. The total of intervention and follow-up period vary from 14 to 20 months. This time table is summarized in the following chart.

In order to achieve more accurate answers from patients and in turn more reliable results, a member of the research team will administer the SF-12, and questionnaires on proactive coping (UPCC), and self-efficacy (PAM-13 and SE+IN) during a face to face interview, as these might require extra guidance when filling in. This will be done at three time points for each group (before the start of the intervention, at the end of the intervention, and two months after the intervention has ended).

[figure not shown]

Figure 1. This figure depicts the time schedule of this study. The EQ-5D-5L is administered 7 or 8 times, depending on cluster, and is depicted as a square. The Care and Work questionnaire is depicted with an arrow. The questionnaires PAM, SE+IN, SF-12 and UPCC are administered thrice: at the start and end of intervention and two months after ending the intervention (star). The dot represents the HCCQ and adapted NPS at 6 months after the start of the intervention. Focus groups (triangle) are organised per cluster, after finishing the intervention.

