The 'cost and utilization and EQ-5D-L5 questionnaires will be filled in at 7 or 8 different timepoints, which will result in 7 or 8 measurements per participant. Participants are asked if they prefer a questionnaire on paper per post or one per email (using Castor). After receiving the questionnaire participants have one week to fill out the questionnaire. If there is no response, patients are called and offered an interview by phone on the questionnaire. The first interview will be done at the start of the study (t=0). Afterwards information for the questionnaires will be gathered 6 or 7 more times, see figure 1 in §3 study design for an overview and timing of questionnaires. In order to achieve more reliable results, a member of the research team will administer the SF-12 and other secondary study parameter questionnaires that might require extra guidance, during a face to face interview at three time points (before the start of the intervention, at the end of the intervention, and three months after the intervention has ended).

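### For SF-12, UPCC, PAM-13 and SE+IN, the section 6 trend-plus-exposure model cannot usefully estimate an intervention effect from the three scheduled visits

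*Protocol*

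**What the plan says.** Section 6 (Statistical analysis, quantitative data) describes one multilevel generalised linear model with patient, practice and randomised group as levels. It adjusts for time from the start of the study, "with an interaction between cluster and time so that each cluster had its own underlying time trend", and for "total time on the randomised intervention, with time before intervention given as zero (continuous". No on/off intervention term is named, and no outcome is exempted. The section does not say whether practice terms are fixed or random, or how exposure is coded after month 12.

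Section 3 (Study design) fixes the switch times: "The first switch will be after 2 months ($t=2$). Every subsequent 2 months a next group of general practices will switch to the intervention". The four psychological questionnaires are given "before the start of the intervention, at the end of the intervention, and two months after the intervention has ended". The Figure 1 caption has them "administered thrice: at the start and end of intervention and two months after ending the intervention (star". Section 5.1.1 instead puts the last visit "three months after the intervention has ended". None of these places gives the questionnaires at t=0.

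On exposure, section 3 points both ways. It says "All groups will continue with the intervention as described in this protocol for a total of 12 months", followed by usual care, but it also counts every timepoint after the switch as intervention period.

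**The concern.** A model with a practice-specific trend needs either repeated control-period measurements in the same practice, or control and intervention measurements at the same calendar time in different practices. These four questionnaires have neither. Each practice has one pre-intervention visit, so its control trend is unobserved. First visits fall in months 2 to 8 and later visits in months 14 to 22, so the staggered start never sets a control measurement beside an intervention one.

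Self-efficacy, proactive coping and SF-12 quality of life are named secondary outcomes. Applied as written, the model gives them no estimate, a very imprecise one, or one that depends on how scores move in the short interval after the intervention ends. Which of these occurs depends on coding choices that section 6 leaves open.

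**Working it through.** The protocol gives no figure to reproduce here. The check concerns what the stated model can identify.

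**Inputs.**
- 20 practices in four groups of five, switching at s = 2, 4, 6, 8 (section 3).
- "We aim to include an average of 10 patients per cluster" (section 3).
- ICC 0.1 (section 4.4).
- Visits at s, s+12 and s+14.
- Assumed: total SD 1, within-patient correlation (given practice) 0 or 0.5, no dropout.

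The residual variance of a practice mean is then 0.9/10 = 0.09 at correlation 0, or 0.45/10 = 0.045 at correlation 0.5.

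**Calendar overlap.** First visits: months 2, 4, 6, 8. End visits: 14, 16, 18, 20. Last visits: 16, 18, 20, 22. No first visit coincides with a later one.

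**Case A: exposure keeps accruing, first visit at the switch.** Exposure is E = 0, 12, 14 at t = s, s+12, s+14, so E = t - s in every row.
- *Fixed practice intercepts and trends.* E is the sum of the 20 practice trend columns minus s times each practice intercept column. The 60-row design has rank 40 with 41 columns, so the coefficient is not estimable. A third visit at s+15 gives the same rank. With fixed intercepts and one common trend the rank is 21 of 22.
- *Random practice intercepts, common trend.* The mean is a + bt + θ(t - s) = a + (b+θ)t - θs. Within a practice only b+θ is seen; θ is separated from b only by how levels differ with switch month.
  - The switch months have sum of squares 5 × (9+1+1+9) = 100 across practices.
  - The visit times have sum of squares about 114.7 within a practice.
  - Correlation 0: var(θ) = (0.1 + 0.09/3)/100 + 0.09/(20 × 114.7) = 0.00134, so SE(12θ) = 12 × 0.0366 = 0.44.
  - Correlation 0.5: var(θ) = (0.1 + 0.045 + 0.045/3)/100 + 0.045/(20 × 114.7) = 0.00162, so SE(12θ) = 0.48.
- *Random practice intercepts, practice trends.* Generalised least squares gives 0.63 and 0.58.
- *95% half-widths.* From 1.96 × 0.44 = 0.86 SD to 1.96 × 0.63 = 1.23 SD.

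**Case B: exposure capped at 12, or an on/off term.** E = 0, 12, 12. With fixed practice intercepts and trends the rank is 41 of 41. Within a practice:
- y14 - y12 = 2b
- y12 - y0 = 12b + 12θ
- so 12θ = (y12 - y0) - 6 × (y14 - y12)

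The two-month segment after the intervention is taken as the secular trend and multiplied by 12/2 = 6. A fade of 0.1 SD there contributes -6 × (-0.1) = +0.6 SD to the apparent benefit; a late gain subtracts in the same way. The weights are -1, +7, -6 (squares sum to 86), so the SE is √(0.09 × 86/20) = 0.62 or √(0.045 × 86/20) = 0.44. With random intercepts it is 0.34-0.46. With the three-month timing of section 5.1.1 the multiplier is 12/3 = 4, which is smaller but has the same defect.

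**Case C: first visit half a month before the switch, exposure accruing.** Rank is restored, but the SE is 11-15 SD with fixed practice intercepts and about 0.46-0.64 SD with random ones.

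**Plain visit contrast, for reference.** √(2 × 0.09/20) = 0.095 or √(2 × 0.045/20) = 0.067, about 0.07-0.10 SD. This is the SE of an uncontrolled before-after change, which is a different quantity.

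**The case against.** A reader might infer that the model cannot be fitted at all for these outcomes. The protocol does not support that. Exact aliasing needs three things together: exposure accruing past month 12, a first visit exactly at the switch, and fixed practice (or group) intercepts. Section 6 describes practice and group as levels of a multilevel model, most naturally random. Section 3 ends the intervention at 12 months and mostly places the first visit before the start. Relaxing any one of the three makes the coefficient estimable.

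It can also be said that section 6 lists time on intervention among the adjustments and does not call it the effect, that an on/off term may be intended, and that such coding belongs in a statistical analysis plan. The coding may be left to that plan. But section 6 itself fixes practice trends for all quantitative data, and an on/off term takes the values of Case B up to scale, with the same sixfold weight on the post-intervention segment under fixed practice terms.

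A second tempting inference is that a simple visit comparison is many times more precise. The SEs belong to different estimands, so the ratio is not a precision gain for the same effect.

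The strongest objection is to the remedy: before-after change is the kind of evidence that section 1 calls promising but not convincing in the pilot, citing regression to the mean. That stands, and it limits what may be claimed from these outcomes.

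**Conclusion.** The concern holds in a limited form. No reading of section 6 fits these four questionnaires: the effect is either not estimable (rank 40 of 41, under the three conditions together), or rests on level differences between four start groups (SE about 0.44-0.63 SD), or is estimable with capped or on/off exposure (SE about 0.34-0.62 SD) but, under fixed practice terms, takes post-intervention fade for secular trend. The SEs depend on equal practices of 10, ICC 0.1, within-patient correlation 0 to 0.5, no dropout, no separate group variance and a third visit at two months. Dropout or a group variance would raise them. The rank result and the sixfold weight do not depend on the ICC or the correlation. The point does not extend to the EQ-5D-5L, which is measured from t=0 and 7 or 8 times.

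**What to change.** In section 6, give SF-12, UPCC, PAM-13 and SE+IN their own model: visit as a three-level factor (before, end of intervention, after the intervention), random patient and practice effects, and no calendar-trend or time-on-intervention terms. Report the end-of-intervention and post-intervention changes from the first visit as uncontrolled within-patient changes, not as randomised intervention effects. State that they include calendar trend and regression to the mean, the limitation that section 1 names for the pilot. Keep the trend model for outcomes measured 7 or 8 times. Reconcile the two-month and three-month timings of the last visit between sections 3 and 5.1.1.

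The cost is one paragraph and no new data. The downside is that these outcomes then support only a descriptive before-after conclusion, which is all that this schedule can deliver.
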